8.7.5 Early vs. late relapse after DLBCL diagnosis

Patients having an 'early relapse' or 'late relapse' after their initial DLBCL diagnosis will be summarized. The following definitions will apply:

- Early relapse after initial DLBCL diagnosis: relapse ≤ 12 months after initial DLBCL diagnosis.
- Late relapse after initial DLBCL diagnosis: relapse > 12 months after initial DLBCL diagnosis.

The 'Date of initial diagnosis of DLBCL' and the 'Date of first progression/relapse' can be found on the 'Diagnosis of DLBCL' eCRF page.

The following imputation rules will be applied in the situation of partially completed dates:

Table 11: Imputation rules for the 'Date of initial diagnosis of DLBCL' and the 'Date of first progression/relapse'

Component of the Date			Variable	
DD	MMM	YYYY	Date of initial diagnosis of DLBCL	Date of first progression/relapse
✓	✓	✓	No imputation	No Imputation
x	✓	✓	1 st day of the month	Last day of the month
x	x	✓	No imputation	No imputation
x	x	x		

- If day and month are missing, but only the year is present for one or both variables required the patient will be assigned to the category 'Late relapse after initial DLBCL diagnosis' if the difference between the year for the 'Date of initial diagnosis of DLBCL' and the year for the 'Date of first progression/relapse' is two years or higher. In case the difference for the years is only one year the relapse category after initial DLBCL diagnosis will be considered as 'Unknown'. In case the year is the same for both variables the patient will be assigned to the category 'Early relapse after initial DLBCL diagnosis'
- If the relapse category cannot be determined, the patient will be considered as 'Unknown'.

8.7.6 Non-study anti-DLBCL treatment

Data on non-study anti-DLBCL treatments will be provided for patients who are still on any study drug, and for patients who have already discontinued the treatment (based on the ‘*Other Anti-Neoplastic Therapies after end of Study Drug Treatment*’ and “*Concurrent Anti-Neoplastic Therapies Medications*” eCRF pages). The following summaries will be presented for both the FAS and the SAF:

- The number (%) of patients who received non-study cancer treatment prior to study treatment discontinuation.
- The number (%) of patients who received non-study cancer treatment after study treatment discontinuation.
- The number (%) of patients who received non-study cancer treatment without a documented radiological progression as per CHESON Criteria.
- The type of anti-cancer treatment received by ATC level 2 class and preferred name.
- Time to start of non-study anti-cancer treatment.
- Therapy line of non-study anti-cancer treatment.
- Reason for stopping non-study anti-cancer treatment.

Time to start of anti-cancer therapy is defined as (start date of anti-cancer treatment – date of last dose of study treatment + 1). In case the anti-cancer therapy started before the last dose of study treatment the time will be set to zero. If the start date of anti-cancer treatment is missing, then the time to start of anti-cancer treatment for that patient will be missing. Listings on other non-study cancer treatments will be presented for the SAF.

8.8 Pre-Medication for MOR00208 infusion

Due to the occurrence of infusion related reactions (IRRs), patients may receive pre-medications administered prior to MOR00208 infusions. These may include antipyretics, histamines, glucocorticosteroids, and meperidine. Pre-medications and their doses will be listed for all patients who received either LEN or MOR00208 (SAF population).

8.9 Study treatment

8.9.1 Treatment cycles

The patients will be administered study treatment according to cycles. Each Treatment cycle will consist of 28 days. The duration of exposure for each study treatment drug is defined according to regimen as outlined below.

MOR00208:

The planned administration of MOR00208 is as follows:

- Cycle 1: Day 1, Day 4 (loading dose), Day 8, Day 15, Day 22.
- Cycle 2: Day 1, Day 8, Day 15, Day 22.
- Cycle 3: Day 1, Day 8, Day 15, Day 22.
- Cycle 4 onwards: Day 1 and Day 15.

MOR00208 will be administered at a dose of 12.0 mg/kg IV. Dose reductions of MOR00208 are not allowed during the course of the study. Unless contraindicated the MOR00208 treatment should continue, even if the patient discontinues LEN treatment.

LEN:

The planned administration of LEN is as follows:

- Cycle 1 to Cycle 12: 25 mg oral LEN daily on days 1-21 of the respective cycle.
- Reduced LEN doses after reduction of the total daily dose (see Section 8.9.3) will also be administered on days 1-21 until Cycle 12.

8.9.2 Exposure

6.1.1 Duration of exposure to study drug

Exposure to study treatment and each study drug will be summarized for the FAS and the SAF.

Duration of exposure (days) = (last date of exposure to study drug) – (date of first administration of study drug) + 1.

Taking into account the period of rest between infusions, the **last date of exposure** is defined as follows:

- For MOR00208: When the study drug is administered over several regular doses with regular time intervals, the last date of exposure is identified according to the planned dose schedule of the cycle. If no rest period is included in the cycle then the last date of exposure is: (last date of administration of the study drug) + (length of time interval-1). **Length of time interval:** 7 days in Cycle 1-3 and 14 days from Cycle 4 onwards. In case a patient dies before the end of the time interval the date of death will be used to truncate the time interval, i.e., in this case the last date of exposure will be set as the date of death.
- For LEN, the last date of exposure will be defined as the last date of administration. Thus, planned dose interruptions between days 22 to 28 of each cycle, as per protocol, will not be considered. That is, only day 1 to 21 will be considered as being exposed to LEN.

7.1.1 Duration of exposure to study treatment

Duration of exposure (days) = (last date of exposure of all the study drugs) – (date of first administration of study treatment) + 1.

The definition of exposure is specified in the section *duration of exposure to study drug*.

8.1.1 The duration of exposure to study treatment / drug will be calculated in months.

9.1.1 Exposure analysis

- The number of patients completing each cycle will be summarized. A patient is considered to have completed a cycle for MOR00208 if he/she was compliant for all MOR00208 infusions during the cycle. A patient is considered to have completed a cycle for LEN if he/she was compliant (see Section 8.9.6) for LEN administration during the cycle.
- Summary statistics will be displayed. The duration of exposure will also be summarized according to the following categories: Month 1-2, 3-4, 5-6, 7-8, etc.
- Number of infusions with MOR00208 will be summarized as follows:
 - The total number of MOR00208 infusions will be summarized
 - The number (%) of patients belonging to the following categories will be derived: 0-2 infusions, 3-4 infusions, 5-6 infusions, 7-8 infusions, etc.

8.9.3 Dose reduction

Dose reductions are only possible for LEN, but not for MOR00208. The number (%) of patients with any dose reduction will be summarized for LEN. The number (%) of patients with a reduction to a minimum of 20 mg, 15 mg, 10 mg, or 5 mg without having completely discontinued treatment will be shown. Moreover, the number (%) of patients who had no reduction at all or only a reduction to 20 mg (but not lower) will be summarized.

8.9.4 Dose interruption

The number (%) of patients with temporary interruptions and the associated reasons will be summarized for both study drugs.

8.9.5 Permanent discontinuations

A summary of patients who discontinued permanently will be provided for both study drugs. The reasons for permanent discontinuation from the study drug will be summarized for each study drug.

8.9.6 Compliance

10.1.1 MOR00208

Compliance for MOR00208 will be calculated by taking the actual MOR00208 infusion dose divided with the planned MOR00208 infusion dose. Compliance will be summarized per single infusion and per cycle:

- MOR00208 compliance per **single infusion**: if the MOR00208 dose administered is $\geq 80\%$ and $\leq 120\%$ of the planned dosage.
- MOR00208 compliance **per cycle**: if this quantity is $\geq 80\%$ and $\leq 120\%$ of the planned dosage for the cycle, then the patient will be considered compliant for that cycle.

11.1.1 LEN

LEN is taken for the first 21 days of each cycle. Patients experiencing a transient treatment interruption, e.g., due to toxicities, or patients undergoing treatment discontinuation may take LEN for less than 21 days, which would not be considered as non-compliance. Similarly, a planned reduction of the *Total Daily Dose* will not be considered as non-compliance.

For some patients and Cycles the *Total Daily Dose* will be reached by combining tablets of two different *Dose Strengths*. Compliance will be calculated as follows:

If $(\text{total used dose})/(\text{total planned dose})$ is between 80% and 120%, both inclusive, of the assigned dosage during a particular cycle, then the patient is considered compliant for LEN during that particular cycle. The *Total Planned Dose* and the *Total Used Dose* will be derived as follows:

For patients who did not experience a dose change or treatment interruption (as indicated on the eCRF page '*Lenalidomide Dosing Record*):

- The **Total Planned Dose** will be calculated as follows:
 $21 \times \text{Total Daily Dose}$ (as entered on the eCRF page '*Lenalidomide Dosing Record*').
- The **Total Used Dose** will be calculated as follows:
 - For patients and cycles in which the Total Daily Dose is reached by taking one capsule only:

STATISTICAL ANALYSIS PLAN

 MorphoSys AG
 MOR208C203

Total Used Dose = (Number of Capsules Dispensed - Number of Capsules Returned) x Dose Strength.

For patients and cycles in which the Total Daily Dose is reached by combining two or more capsules of different Dose Strengths (e.g., Dose Strength 1 and Dose Strength 2):

Total Used Dose = [(Number of Capsules of Dose Strength 1 Dispensed - Number of Capsules of Dose Strength 1 Returned) x Dose Strength 1] + [(Number of Capsules of Dose Strength 2 Dispensed - Number of Capsules of Dose Strength 2 Returned) x Dose Strength 2].

For patients who experienced a dose change, treatment interruption or treatment discontinuation (as indicated on the eCRF page '*Lenalidomide Dosing Record*'):

- The **Total Planned Dose** will be calculated as follows:
 - Patients who required a dose change or interruption and did not start LEN treatment (with same or changed dose) before completion of that particular Cycle the dose change/interruption happened:

$\text{Min}[21, (\text{Dosing Stop Date} - \text{Dosing Start Date} + 1)] \times \text{Total Daily Dose}$ (as entered on the eCRF page '*Lenalidomide Dosing Record*').

Note: Separate log lines on the eCRF page '*Lenalidomide Dosing Record*' may exist for patients who reach the *Total Daily Dose* by combining capsules of different dose strengths. In this case, *Total Daily Dose*, *Dosing Start Date* and *Dosing Stop Date* are identical across the different eCRF log lines and only information from one log line will be used. In rare cases it may happen that actually $\text{Dosing Stop Date} - \text{Dosing Start Date} + 1 > 21$, in this case the planned dose is calculated with 21 days only.
 - Patients who required a dose change / treatment interruption, and started the new *Total Daily Dose* / re-initiated treatment (in case of interruption) before completion of that particular Cycle the dose change/interruption happened:

E.g., for one dose reduction, or one interruption:

$[(\text{Dosing Stop Date for Total Daily Dose 1} - \text{Dosing Start Date for Total Daily Dose 1} + 1 \text{ Day}) \times \text{Total Daily Dose 1}] + [(\text{Dosing Stop Date for Total Daily Dose 2} - \text{Dosing Start Date for Total Daily Dose 2} + 1 \text{ Day}) \times \text{Total Daily Dose 2}]$.

Notes:

STATISTICAL ANALYSIS PLAN

MorphoSys AG
MOR208C203

- Separate log lines on the eCRF page '*Lenalidomide Dosing Record*' will show the *Total Daily Dose* before and after dose change, or before and after treatment interruption, respectively.
- In case of treatment interruption *Total Daily Dose 1* and *Total Daily Dose 2* (in case of only one interruption) will be identical.
- Separate log lines may exist showing the identical information on *Dosing Start Date*, *Dosing Stop Date*, and *Total Daily Dose* in case the *Total Daily Dose* is reached by combining different *Dose Strengths*. In this situation, only the information from one eCRF log line will be used.

- The **Total Used Dose** will be calculated as follows:
 - Patients who required a dose change or treatment interruption, and did not start LEN treatment (with same or changed dose) before completion of that particular Cycle the dose change/interruption happened:
 - For patients and Cycles in which the *Total Daily Dose* (as entered in the eCRF page '*Lenalidomide Dosing Record*') is reached by taking one capsule only: *Total Used Dose* = (Number of Capsules Dispensed - Number of Capsules Returned) x Dose Strength.
Note: Only one log line on the eCRF page '*Lenalidomide Dosing Record*' will exist for this situation.
 - For patients and cycles in which the *Total Daily Dose* (as entered in the eCRF page '*Lenalidomide Dosing Record*') is reached by combining capsules of different *Dose Strengths*:
E.g., Dose Strength 1 and Dose Strength 2:
$$\textit{Total Used Dose} = [(\text{Number of Capsules of Dose Strength 1 Dispensed} - \text{Number of Capsules of Dose Strength 1 Returned}) \times \text{Dose Strength 1}] + [(\text{Number of Capsules of Dose Strength 2 Dispensed} - \text{Number of Capsules of Dose Strength 2 Returned}) \times \text{Dose Strength 2}].$$

Note: Several log lines with the same *Dosing Start Date* on the eCRF page '*Lenalidomide Dosing Record*' exist for this situation (representing the different dose strengths).
 - Patients who required a dose change / treatment interruption, and started the new *Total Daily Dose* / re-initiated treatment (in case of interruption) before completion of that particular Cycle the dose change/interruption happened:
 - Change of the *Total Daily Dose* within a particular Cycle:

STATISTICAL ANALYSIS PLAN

 MorphoSys AG
 MOR208C203

Capsules of only one dose strength or a combination of several dose strengths might be used before or after dose change to reach the targeted *Total Daily Dose*. The *Total Used Dose* will be calculated as follows:

E.g., for capsules of two different dose strengths before and after dose change:

$$\begin{aligned} \text{Total Used Dose} = & [(\text{Number of Capsules of Dose Strength 1 Dispensed before dose change} - \text{Number of Capsules of Dose Strength 1 Returned before dose change}) \times \text{Dose Strength 1}] + [(\text{Number of Capsules of Dose Strength 2 Dispensed before dose change} - \text{Number of Capsules of Dose Strength 2 Returned before dose change}) \times \text{Dose Strength 2}] + \\ & [(\text{Number of Capsules of Dose Strength 1 Dispensed after dose change} - \text{Number of Capsules of Dose Strength 1 Returned after dose change}) \times \text{Dose Strength 1}] + [(\text{Number of Capsules of Dose Strength 2 Dispensed after dose change} - \text{Number of Capsules of Dose Strength 2 Returned after dose change}) \times \text{Dose Strength 2}]. \end{aligned}$$

Note: In case only one dose strength is being used before or after changing the *Total Daily Dose*, one of the summands (e.g., the terms for Dose Strength 2) will become 0.

- Interruption and re-initiation of treatment within a particular Cycle: Capsules of only one dose strength or a combination of several dose strengths might be used to reach the targeted Total Daily Dose. The Total Used Dose will be calculated as follows (e.g., for capsules of two different dose strengths):

$$\begin{aligned} \text{Total Used Dose} = & [\text{Number of Capsules of Dose Strength 1 Dispensed before dose change} \times \text{Dose Strength 1}] + [\text{Number of Capsules of Dose Strength 2 Dispensed before dose change} \times \text{Dose Strength 2}] + \\ & [\text{Number of Capsules of Dose Strength 1 Returned after dose change} \times \text{Dose Strength 1}] + [\text{Number of Capsules of Dose Strength 2 Returned after dose change} \times \text{Dose Strength 2}]. \end{aligned}$$

Notes: The *Total Daily Dose* before and after interruption in a particular Cycle is represented in separate log lines on the eCRF page '*Lenalidomide Dosing Record*'.

- The following applies if the *Total Planned Dose* is 0 for an entire Cycle:

-
- If the **Total Used Dose** is 0 for the Cycle, the patient will be considered as compliant for that particular Cycle.
 - If the **Total Used Dose** is not 0, the patient will be considered as non-compliant for that particular Cycle.

Listings showing eCRF entries on LEN dosing records, MOR00208 dosing administration, and MOR00208 infusion details will be produced (for the SAF). A listing will be generated showing the compliance per cycle for each individual for both LEN and MOR00208 (for the SAF).

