16. ADDENDUM 1.0

16.1 Compliance

The compliance for MOR00208 and LEN as outlined in Section 8.9.6 is summarized by Cycle. Boxplots showing the distribution of compliance within the patient population will be produced. The analyses will be performed for both the FAS.

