16.2 Relative dose intensity

The dose intensity of LEN and MOR00208 as defined below will be summarized by Cycle. Boxplots will be generated showing the distribution of the relative dose intensity. The analyses will be conducted using the FAS.

The relative dose intensity for LEN is derived as follows:

- „Planned dose“ for each Cycle: 25 mg x 21 days = 525 mg per Cycle (ignoring dose change, interruptions, discontinuations)
- „Used dose“ for each Cycle: X mg total daily dose x number of pills taken in that Cycle (pills returned – pills dispensed will be used as surrogate for pills taken)
- Relative Dose Intensity by Cycle: „Used dose“ / „Planned dose“ x 100
- A boxplot showing the distribution of the Relative Dose Intensity by Cycle will be generated

The relative dose intensity for MOR00208 is derived as follows:

- „Planned dose“ for a particular Cycle: 250 ml x planned number of infusions for a particular Cycle (varies depending on the Cycle)
- Infusion interruptions and skipped doses will be ignored when determining the „planned dose“
- „Used dose“ for a particular Cycle: sum of actual volume administered across all infusions of a Cycle
- Relative Dose Intensity by Cycle: „Used dose“ / „planned dose“ x 100
- A boxplot showing the distribution of the Relative Dose Intensity by Cycle will be generated

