20.5 Relationship between LEN dose intensity and efficacy

20.5.1 DoR and ORR in subgroups of varying relative cumulative LEN exposure

Patients will be categorized according to their relative cumulative LEN dose, which will be derived as follows:

Relative cumulative LEN dose intensity = (cumulative total used dose / reference cumulative dose) x 100.

- The reference cumulative dose represents the cumulative LEN dose a patient is supposed take until he/she progresses per IRC (for summaries of DoR; see below) or until he/she reaches a CR or PR (for summaries of ORR; see below):
 - Example 1 for a summary of DoR: a patient who only progresses later than Cycle 12 experiences the following reference cumulative dose: 12 months x 21 days x 25 mg LEN per day = 6300 mg LEN
 - Example 2 for a summary of DoR: a patient who progresses on Cycle 7, Day 10 experiences the following reference cumulative dose: (6 months x 21 days x 25 mg LEN per day) + (10 days x 25 mg LEN per day) = 3400 mg LEN
 - Example 3 for a summary of ORR: a patient who reaches a CR at Cycle 3 Day 25 experiences the following reference cumulative dose: 3 months x 21 days = 1575 mg LEN
- The cumulative total used dose represents the cumulative LEN dose a patient has actually ingested until he/she progresses per IRC (for summaries of DoR) or until he/she

reaches a CR or PR (for summaries of ORR). The derivation of the total used dose for LEN is described in Section 8.9.6.

Based on the relative cumulative LEN dose intensity, the following patient subgroups will be defined:

- Patients with relative cumulative LEN dose intensity of <50%
- Patients with relative cumulative LEN dose intensity of 50%-80% (inclusive)
- Patients with relative cumulative LEN dose intensity of >80%

The following will be analyzed for the subgroups defined above:

- Summary of DoR including a Kaplan-Meier plot (see Section 10.3)
- Best objective response rate and rates for best response of CR/PR/SD/PD/not evaluable assessment (see Section 9)

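### Two lenalidomide dose formulas in the SAP are wrong as printed: 8.9.6 adds returned capsules after a same-dose interruption, and 16.2 reverses the subtraction and multiplies by the daily dose

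*SAP*

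**What the plan says.** SAP 8.9.6 (LEN part, printed as 11.1.1) calls a patient compliant in a cycle if total used dose divided by total planned dose lies between 80% and 120% inclusive. Planned dose comes from dosing start and stop dates. Used dose comes from capsule counts.

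For a cycle with no change or interruption, and for an interruption without restart in that cycle, used dose with one capsule strength is "Number of Capsules Dispensed - Number of Capsules Returned) x Dose Strength". With two strengths the same difference is taken for each strength and summed. A change of daily dose within the cycle uses the same differences, separately before and after the change.

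The exception is interruption and restart within a cycle. The printed formula has four terms joined by plus signs: capsules dispensed before, for strengths 1 and 2, and capsules returned after, for strengths 1 and 2 ("Number of Capsules of Dose Strength 1 Returned after dose change"), each times its strength. Capsules returned before and dispensed after do not appear. Section 8.9.6 also says that separate log lines show the daily dose "before and after dose change, or before and after treatment interruption, respectively", and that the two daily doses are identical when there is one interruption.

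SAP 16.2 divides used dose by 525 mg per cycle. Used dose is "X mg total daily dose x number of pills taken in that Cycle", and the number of pills taken is obtained by starting from pills returned and subtracting: "pills dispensed will be used as surrogate for pills taken".

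**The concern.** A returned capsule was not taken, so adding it cannot give a used dose. In 16.2 the difference is negative whenever anything was taken. The daily-dose multiplier is right only if one capsule makes up the daily dose, and 8.9.6 says that some patients and cycles combine two strengths.

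The 8.9.6 quantity is used in four places:

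- the per-patient, per-cycle compliance listing;
- the by-cycle summary and boxplots in 16.1 ("The compliance for MOR00208 and LEN as outlined in Section 8.9.6 is summarized by Cycle");
- the count of completed cycles in the exposure analysis under 8.9.2 ("A patient is considered to have completed a cycle for LEN if he/she was compliant");
- the relative cumulative dose groups in 20.5.1 (<50%, 50-80%, >80%) used for DoR and ORR ("The derivation of the total used dose for LEN is described in Section 8.9.6").

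Under single dispensing the 8.9.6 error raises apparent exposure in exactly the patients who missed doses, which works against a dose-efficacy comparison. The 16.2 error stays within the by-cycle relative dose intensity summary and boxplots.

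**Working it through.** **Stated figures first.** 16.2: 25 x 21 = 525 mg. 17.7 worked example: (525 + 525 + 420 + 50) / 91 = 16.7 mg. 20.5.1, twelve cycles: 12 x 21 x 25 = 6300 mg. All reproduce. The SAP gives no worked number for either disputed formula, so the capsule counts and strength splits below are assumptions.

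**8.9.6, one dispensing per cycle.** Take 21 capsules of 25 mg dispensed at the start and R returned, with intake exactly as planned.

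- Printed used dose: (21 + R) x 25.
- True used dose and planned dose: (21 - R) x 25.

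| R | Printed (mg) | True = planned (mg) | Printed compliance |
|---|---|---|---|
| 0 | 525 | 525 | 100% |
| 1 | 550 | 500 | 110% |
| 2 | 575 | 475 | 121.1% |
| 7 | 700 | 350 | 200% |

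True compliance is 100% in every row. A patient who took only 7 of 14 planned capsules (14 returned) scores (21 + 14) x 25 / 350 = 250% instead of 175 / 350 = 50%.

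**8.9.6, separate dispensing before and after.** Printed: (dispensed before + returned after) x 25. True: (dispensed before - returned before + dispensed after - returned after) x 25.

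- 7 dispensed before, 7 after, none returned: 7 x 25 = 175 mg against 14 x 25 = 350 mg, or 50%.
- 21 dispensed and 14 returned before, 7 dispensed after: 21 x 25 = 525 mg against (21 - 14 + 7) x 25 = 350 mg, or 150%.

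**20.5.1, one dispensing per cycle.** The reference dose stays at 25 mg whatever reductions occur.

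| Case | Reference (mg) | True | Printed | Group changes? |
|---|---|---|---|---|
| 2 cycles at 25 mg, 7 doses missed | 1050 | 875 = 83.3% | 1225 = 116.7% | No |
| 2 cycles at 25 mg, 9 missed (5 + 4) | 1050 | 825 = 78.6% | 1275 = 121.4% | Yes, at 80% |
| 12 cycles at 25 mg, 7 missed | 6300 | 6125 = 97.2% | 6475 = 102.8% | No |
| Cycle 1 at 25 mg, 11 cycles at 20 mg, 6 missed | 6300 | 5025 = 79.8% | 5265 = 83.6% | Yes, at 80% |

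In the last row the dispensed total is 525 + 11 x 420 = 5145 mg, and the 6 missed doses are 120 mg, subtracted or added. Counting Cycle 3 Day 1 itself in the second row gives 850 / 1075 = 79.1% against 1300 / 1075 = 120.9%, so the crossing remains.

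**16.2.**

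- 25 mg as one capsule, fully taken: (0 - 21) x 25 / 525 = -100%. Correct value: 100%.
- 20 mg/day as 15 + 5 mg, fully taken, sign corrected: 42 x 20 / 525 = 160%. Correct value: (21 x 15 + 21 x 5) / 525 = 80%.

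**The case against.** The wording is not in dispute. The case against concerns its weight.

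- **Missing terms.** Protocol 6.8 dispenses LEN by 28-day cycle, and Table 5 allocates it only on Day 1. Dispensed before minus returned after would then be complete and only the sign is wrong. This is fair, and it makes the separate-dispensing figures illustrative only. It leaves the sign error intact.
- **Narrow branch.** The interruption must end within the same cycle at the same dose, with at least two capsules returned to breach 120% under single dispensing. Protocol Table 2 sends restarts to the next lower level, where the formula is right. The restarts in Table 3 at an unchanged dose concern thromboembolic events and tumour flare. Protocol 6.6.2 also ties resumption to the next scheduled visit. All this stands, and the documents give no frequency for the branch.
- **Constructed group changes.** Most single interruptions move nobody between 20.5.1 groups. The crossings shown need nine missed doses in two cycles, or a patient just below 80%, and none is at 50%. This stands.
- **Visible errors.** A negative dose intensity or a 200% compliance value should be noticed in the outputs. That is likely for the negative sign. It is less certain for 121% or a doubled dose, which are positive and could pass as over-use.
- **Misread sign.** The formula was read from a PDF. The neighbouring formulas kept their minus signs while all three joins here are plus signs, so a misreading is unlikely but not excluded.

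**Conclusion.** The concern holds. Both formulas give wrong values when followed as printed.

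In 8.9.6 an adherent patient with a same-dose interruption reads 121% with two returned capsules and 200% with seven, assuming one dispensing of 21 x 25 mg. With separate dispensing the error can go either way. In 16.2 every cycle with any intake has the wrong sign, and cycles with two capsules a day are doubled as well.

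The consequences are limited to LEN compliance, completed cycles, the 16.1 and 16.2 displays and, in uncommon patterns, the 20.5.1 subgroups. The primary ORR, the main PFS, DoR and OS analyses, the date-based dose intensity in 17.7 and the dose-reduction groups in 20.5.2 are unaffected. Whether the programs followed the printed text cannot be told from the documents. The correction should be made, but it does not threaten the main conclusions.

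**What to change.** In 8.9.6, replace the formula for interruption and restart within a cycle with the sum, over all log lines and capsule strengths in that cycle, of (dispensed - returned) x capsule strength. This is right whether capsules are recorded once or separately around the interruption. Changing only the plus signs would be right only under single dispensing.

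In 16.2, use the same sum divided by 525 mg.

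Then check the programs against the corrected text. If the printed formulas were coded, re-run LEN compliance (8.9.6 and 16.1), completed cycles, the 16.2 summary and boxplots, and the 20.5.1 DoR and ORR summaries. The cost is two short text corrections and a program check, plus a few re-run outputs if needed.
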